9.6.2 Pharmacokinetics

Model-based PK Summary

Evaluation of the effects of donepezil on the PK of MK-1942 in AD patients

At each dose level, individual values of the plasma C_{max} of MK-1942 on the last day of a titrated treatment regimen after co-administration with donepezil to AD patients, as well as the C_{max} of MK-1942 after administration of MK-1942 alone to HEV in MK-1942-004 will

be natural log transformed and analyzed in an ANOVA model. The model contains one factor for treatment (MK-1942 alone in HEV, MK-1942+donepezil in AD patients).

Ninety percent (90%) CIs will be constructed for GMRs (MK-1942 + donepezil in AD patients/ MK-1942 alone in HEV) from the model after back-transformation. The hypothesis that the plasma C_{max} of MK-1942 determined on the last day of a titrated treatment regimen (Day 21 [28]) when co-administered with donepezil to AD patients is similar to the C_{max} obtained following administration of MK-1942 alone to HEV (MK-1942-004) will be supported if the 90% CI for the true GMR (MK-1942 + donepezil in AD / MK-1942 alone in HEV) is contained within the interval (0.5, 2.0). Ninety-five percent (95%) CIs for the least squares means by treatment will be constructed on the natural log scale and will reference a t-distribution. Exponentiating the least square means and the lower and upper limits of these confidence intervals will yield estimates for the population geometric means and confidence intervals about the geometric means on the original scale. Similar analyses will be conducted with MK-1942 AUC₀₋₁₂ and C_{trough}.

Evaluation of the effects of MK-1942 on the PK of donepezil in AD patients

Separately for each PK parameter, individual AUC₀₋₂₄ and C_{max} of donepezil when co-administered with MK-1942 or alone (Day -1) will be natural log transformed and analyzed in a linear mixed effects model. The model contains fixed effect for treatment (MK-1942 and donepezil, donepezil alone) and random effect for subject. Ninety-five percent (95%) CIs for the least squares means by treatment will be constructed on the natural log scale and will reference a t-distribution. Ninety percent (90%) CIs will be constructed for the true GMRs (MK-1942 + donepezil / donepezil alone) from the model after back-transformation.

Descriptive Statistics

Individual values will be listed for each PK parameter by dose level, and the following (non-model-based) descriptive statistics will be provided, if appropriate: N (number of participants with non-missing data), arithmetic mean, standard deviation, arithmetic percent CV (calculated as $100 \times \text{standard deviation} / \text{arithmetic mean}$), median, minimum, maximum, geometric mean, and geometric percent CV (calculated as $100 \times \sqrt{\exp(s^2) - 1}$, where s^2 is the observed variance on the natural log-scale).

Exploratory Analysis

MMSE-2 scores

In order to evaluate the change in cognitive function of AD patients, descriptive summary statistics of the values and the change from baseline values will provided for the MMSE-2 scores obtained at baseline (screening) and from the last day of dosing.

WAIS-R DSST scores

In order to evaluate the change in cognitive function of AD patients, descriptive summary statistics of the values and the change from baseline values will provided for the DSST scores obtained at baseline (Day -1), Day 14, and from the last day of dosing (Day 21 [28])

Concentration-QTc

The average of the triplicate measurements at any time point will be calculated prior to any further analysis. Fridericia's correction to QT ($QTcF = QT / RR^{1/3}$) will be made in order to correct for heart rate. The appropriateness of the correction factor (ie, 1/3) will be assessed via a linear mixed effects model with QTcF as the response variable and RR interval as a covariate and subject as a random effect, using data from the placebo treatment and the predose measurements of the active treatments. A slope estimate close to zero would indicate that Fridericia's correction provides an adequate correction to the original QT data; otherwise, an appropriate transformation on RR will be further explored.

The predose value on Day 1 will serve as baseline for calculating individual change from baseline at each time point. Observed plasma concentrations and observed QTcF change from baseline will be used to investigate the relationship between QTcF and plasma MK-1942 concentrations (placebo data will also be used in this assessment, with the plasma concentration of MK-1942 set to 0). Scatter plots of QTcF change from baseline versus corresponding time-matched MK-1942 concentration will be provided.

The QTcF change from baseline will be further evaluated using a linear mixed effects model with fixed effects for treatment (MK-1942, placebo), time point, continuous effects for QTcF baseline, plasma concentration. A double compound symmetry covariance structure will be assumed. The highest 'safe' drug concentration (C_{safe}), defined as the highest drug concentration whose upper limit of the two-sided 90% confidence interval (equivalent to a one-sided upper 95% confidence limit) of $\Delta\Delta QTcF$ (placebo- baseline- adjusted) less than 10 milliseconds (ms), will be reported. An estimate of the expected mean effect and 90% confidence interval of $\Delta\Delta QTcF$ will also be computed at the observed geometric mean C_{max} for each MK-1942 dose of interest.

Additional modeling of the concentration and QTc data from this study may be conducted later as part of a broader evaluation of MK-1942's QTc prolongation potential. In that case, a separate Modeling Analysis Plan will be written prior to analysis.

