3 HYPOTHESES, OBJECTIVES, AND ENDPOINTS

Hypotheses are aligned with objectives in the Objectives and Endpoints table.

Details of the hypotheses to be tested can be found in Section 9.3.

Objectives	Endpoints
Primary	

Evaluate the safety and tolerability of treatment (MK-1942 co-administered with donepezil) in AD patients with mild-to-moderate cognitive impairment.	
Safety measures (VS, ECGs, clinical chemistry, hematology, urinalysis, targeted neurological exams, Columbia suicide severity rating scale) and Adverse Event reports
Secondary	

Evaluate the effects of donepezil on the PK of MK-1942 in AD patients 
Hypothesis
 
The plasma Cmax of MK-1942 determined on the last day of a titrated treatment regimen (Day 21 [28]) when co-administered with donepezil to AD patients is similar to the Cmax obtained following administration of MK-1942 to HEV from MK-1942-004, Panel C. That is, the true GMR (MK-1942 + donepezil in AD / MK-1942 in HEV) is contained within the interval (0.5, 2.0).	
Cmax, AUC0-12, AUC0-24, Ctrough, Tmax, apparent terminal t1/2, CLss/F, and Vzss/F of MK-1942AUC0-24, Cmax, Ctrough, Tmax for donepezil

Objectives	Endpoints

 Evaluate the effects of MK-1942 on the PK of donepezil in AD patients. Estimation: 
 The true GMRs of plasma PK parameters (AUC₀₋₂₄, C_{max}) for donepezil before and during administration of donepezil + MK-1942 to AD patients will be estimated. 	
Tertiary/Exploratory	

 Evaluate the changes in cognitive function of AD patients by comparing the MMSE-2 and DSST scores obtained at baseline with those from the last day of dosing. Explore the relationship between plasma concentrations of MK-1942 and corrected QT intervals. CCI [REDACTED] Explore the relationships between genetic variation, response to the treatment(s) administered, and mechanisms of disease. Variation across the human genome may be analyzed for association with clinical data collected in the study. 	
 MMSE-2 scores DSST scores QTcF Germline genetic variation

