The plasma PK of MK-1942 following multiple dose co-administration with donepezil will be characterized by determining the C_{max}, T_{max}, C_{trough}, and AUC₀₋₁₂ after the first dose. In addition, C_{max}, T_{max}, C_{trough}, AUC₀₋₁₂, AUC₀₋₂₄, apparent terminal t_{1/2}, CL_{ss}/F, V_{zss}/F and accumulation ratio will be determined at steady state. This will allow doses and dosing regimens in elderly participants with AD to be identified that produce systemic exposures in the predicted efficacious range ^{CCI} [REDACTED] while providing insights into the ability of donepezil to alter the PK of MK-1942.

Similarly, the plasma PK of donepezil following once daily administration will be characterized by determining the C_{max}, T_{max}, and AUC₀₋₂₄ on the day before administration of the first dose of MK-1942 and after 21 (28) days of co-administration. Determining the C_{max} and AUC₀₋₂₄ of donepezil during co-administration with MK-1942 will provide insights into the ability of MK-1942 to alter the PK of donepezil.

Exploratory Endpoints

The Mini-Mental State Exam, edition 2 (MMSE-2) will be administered to AD patients at screening and upon completion of up to 28 days of treatment. The score from the MMSE-2 given at screening will be used as an inclusion criterion, to ensure that AD patients being enrolled fall into the cognitive impairment categories of mild to moderate severity. The MMSE-2 is a 30-point examination evaluating Registration, Orientation to Time, Orientation to Place, Attention, Recall, Language, Repetition, Complex Commands, and Recall tasks. A score between 21 to 26 typically indicates that a subject is experiencing mild cognitive impairment, while scores in the range of 10-20 are indicative of patients with moderate cognitive impairment. This study proposes to enroll individuals with mild to moderate cognitive impairment as indicated by scores between 17 to 26. This range will allow for broader recruitment while reducing the burden on CRU personnel associated with caring for patients with MMSE-2 scores < 17. In addition to its use as a screening tool for identifying

candidate participants as having mild to moderate cognitive impairment, the MMSE-2 will be used as an exploratory endpoint to determine whether the treatment regimen results in any changes from the initial score.

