4.2.2 Rationale for the Use of Comparator/Placebo

Placebo will be used in this trial to allow for an appropriate assessment of the safety data of MK-1942, any impact of MK-1942 treatment on donepezil PK, and to maintain study blinding to reduce bias.

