Ninety percent (90%) CIs will be constructed for GMRs (MK-1942 + donepezil in AD patients/ MK-1942 alone in HEV) from the model after back-transformation. The hypothesis that the plasma C_{max} of MK-1942 determined on the last day of a titrated treatment regimen (Day 21 [28]) when co-administered with donepezil to AD patients is similar to the C_{max} obtained following administration of MK-1942 alone to HEV (MK-1942-004) will be supported if the 90% CI for the true GMR (MK-1942 + donepezil in AD / MK-1942 alone in HEV) is contained within the interval (0.5, 2.0). Ninety-five percent (95%) CIs for the least squares means by treatment will be constructed on the natural log scale and will reference a t-distribution. Exponentiating the least square means and the lower and upper limits of these

confidence intervals will yield estimates for the population geometric means and confidence intervals about the geometric means on the original scale. Similar analyses will be conducted with MK-1942 AUC₀₋₁₂ and C_{trough}.

Evaluation of the effects of MK-1942 on the PK of donepezil in AD patients

Separately for each PK parameter, individual AUC₀₋₂₄ and C_{max} of donepezil after co-administration of MK-1942 and donepezil, or donepezil alone (Day -1) will be natural log transformed and analyzed in linear mixed effect model. The model contains fixed effect for treatment (MK-1942 and donepezil, donepezil alone) and random effect for subject. Ninety-five percent (95%) CIs for the least squares means by treatment will be constructed on the natural log scale and will reference a t-distribution. Ninety percent (90%) CIs will be constructed for the true GMRs (MK-1942 + donepezil / donepezil alone) from the model after back-transformation.

Power

PK:

The estimated pooled, between-subject standard deviations on a log scale for MK-1942 C_{max} on the last day of dosing following administration of 3-mg to 20-mg BID doses of MK-1942 for 5 to 10 days to healthy adults in MK-1942-002 is 0.225. Assuming the standard deviation is 30% higher in AD patients than HEV (ie, the between-subject standard deviation on a log scale for C_{max} is 0.29 in AD patients), if the true GMR (MK-1942+donepezil in AD patients/MK-1942 alone in HEV) is 1.00, with 18 AD patients receiving MK-1942 and donepezil and 6 HEV receiving MK-1942 alone in MK-1942-004, there is a 99% probability that the 90% CI of the GMR will fall within the interval of (0.5, 2.0).

Safety:

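### Section 4.2.2 says placebo is there to assess MK-1942's effect on donepezil PK, but the donepezil ratio is a before/after contrast with no day term and no stated role for the placebo Day 21/28 profiles

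*Combined protocol and SAP*

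**What the plan says.** Section 4.2.2 justifies placebo by the safety assessment and then by "any impact of MK-1942 treatment on donepezil PK, and to maintain study blinding to reduce bias". Donepezil PK is thus a named purpose, separate from safety and blinding.

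The Schedule of Activities takes donepezil profiles on Day -1 and Day 28 (Day 21 if Dose Level 4 is not given). Neither it nor the blood-volume table in Appendix 8 restricts this sampling by arm, so the six placebo patients give both profiles too.

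Section 9.6.2 states that the Cmax and AUC0-24 values "of donepezil when co-administered with MK-1942 or alone (Day -1) will be natural log transformed and analyzed in a linear mixed effects model". On the model terms it says: "The model contains fixed effect for treatment (MK-1942 and donepezil, donepezil alone) and random effect for subject". Section 9.1 ties the reference to the same day: "or donepezil alone (Day -1) will be natural log transformed and analyzed in linear mixed effect model". There is no term for day, arm or arm-by-day.

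Section 3 says the GMRs "for donepezil before and during administration of donepezil + MK-1942 to AD patients will be estimated". The Pharmacokinetic Endpoints text in Section 4.2.1 places the two profiles "on the day before administration of the first dose of MK-1942 and after 21 (28) days of co-administration".

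**The concern.** Every co-administration profile in the model comes from the later day. If the reference is Day -1, as Sections 9.1 and 9.6.2 state, treatment and day are fully confounded. A shift in donepezil exposure over those weeks, from whatever cause, is then reported as an effect of MK-1942.

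Such a shift is possible. Patients take their own prescription, evening takers move to morning dosing on Day -7, and supervised intake starts only on admission at Day -2. With a half-life of about 70 h, Day -1 exposure still reflects home intake. The randomised placebo arm is the part of the trial that can show a change from Day -1 to Day 21/28 without MK-1942. The plan collects those data and does not say how they enter the ratio.

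Elsewhere in Section 9.6.2, the exploratory QTcF model has "fixed effects for treatment (MK-1942, placebo), time point, continuous effects for QTcF baseline, plasma concentration". The secondary donepezil model has neither a placebo contrast nor a time term.

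**Working it through.** The plan states no sample size, power or precision for the donepezil GMR, so there is no figure of its own to reproduce. The 99% in Section 9.9 belongs to the MK-1942 Cmax comparison and does not bear on this point.

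**Inputs from the documents.** 18 patients on MK-1942 and 6 on placebo (Table 1, Table 8); 9 donepezil samples on each of 2 days, which is the 18 per participant in Appendix 8; half-life about 70 h (Section 2.2.4); switch to morning dosing on Day -7 (Section 8.1.8.1); admission on Day -2 and optional home leave on days 5 and 6 of each dose level (Section 8.1.11).

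**Assumed, because the documents give no value.** Within-subject log SD σ of 0.10 to 0.20; within-subject correlation ρ of 0.5 to 0.95; home intake of 70% to 95%; one-compartment kinetics with absorption rate 0.5/h.

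**1. What the planned ratio estimates.** Let θ be the log effect of MK-1942 and δ the log change from Day -1 to Day 28 that has another cause. The mean change is θ + δ in the active arm and δ in the placebo arm. The planned contrast estimates θ + δ, so 100% of the drift remains.

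**2. Counting placebo Day 28 as donepezil alone, without a day term.** The within-patient estimate (θ + δ) has variance 2σ²/18 = σ²/9. The between-arm estimate (θ) has variance (4/9)σ²(1+ρ)/(1−ρ). Inverse-variance weighting leaves this share of δ:

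4 / [4 + (1−ρ)/(1+ρ)] = 0.923, 0.958, 0.987, 0.994 at ρ = 0.5, 0.7, 0.9, 0.95.

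So 92% to 99% of the drift stays.

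**3. Day plus treatment, both arms.** Common drift cancels. Standard errors:

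- Before/after: σ√(2/18) = 0.333σ.
- Day + treatment: σ√[(1+ρ)(1/18+1/6)] = 0.577σ, 0.615σ, 0.650σ, 0.658σ at the same ρ, which is 1.73, 1.84, 1.95, 1.97 times the before/after value.
- Arm, day and arm-by-day: σ√[2(1/18+1/6)] = 0.667σ, or 2.00 times.

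**4. Precision and break-even.** The 90% CI factor is exp(t × SE), with t on 17 df for before/after and, as an approximation, 22 df for day + treatment. The adjusted ratio has the lower mean squared error only if drift exceeds exp√(SE²adj − SE²before/after) − 1.

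| σ | Before/after CI factor | Day + treatment CI factor | Break-even drift |
|---|---|---|---|
| 0.10 | 1.06 | 1.10–1.12 | 4.8–5.8% |
| 0.15 | 1.09 | 1.16–1.19 | 7.3–8.9% |
| 0.20 | 1.12 | 1.22–1.25 | 9.9–12.0% |

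**5. How large drift might be, with no interaction.** The daily carry-over is r = 2^(−24/70) = 0.788. Suppose a fraction f of doses is taken up to Day -3 and all doses afterwards. With fast absorption, Day -1 exposure is 1 − (1−f)r² = 1 − 0.622(1−f) of full steady state. At f = 0.80 this is 0.876, so Day 28/Day -1 is 1/0.876 = 1.14. Superposition with absorption 0.5/h gives:

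| Scenario (Day 28/Day -1) | f = 0.95 | 0.90 | 0.80 | 0.70 |
|---|---|---|---|---|
| Full intake from Day -2 on (worst case) | 1.033 | 1.068 | 1.145 | 1.235 |
| Same fraction f also on leave days | 1.013 | 1.028 | 1.059 | 1.096 |

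The Day -7 switch gives 0.976 (12 h gap) or 1.022 (36 h gap), in switchers only. An absorption rate that matches a Tmax of 3.5 h changes these ratios by at most 0.004.

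**6. Effect on the reading.** At an assumed within-subject CV of 20%, day effects of 1.05, 1.10 and 1.20 alone make the before/after 90% CI exclude 1 with probability 18%, 40% and 84%, against a nominal 10%.

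**The case against.** The planned ratio matches the objective. Section 3 and Section 4.2.1 both frame it as before versus during, and confounding with day is inherent in any before/after design. On that view the only fault is one clause in Section 4.2.2. This stands as a reason to keep the planned ratio; it does not remove the conflict with that clause.

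Drift is probably limited. The donepezil dose must be stable for a month before screening, a trial partner is required, patients are admitted on Day -2 and telephoned daily on leave, and PK uses the Per-Protocol set. The one source the documents describe, the dosing-time switch, gives about 2%, below every break-even value. In the recurring-leave scenario the adjusted ratio wins on mean squared error only at about 80% intake or less (σ 0.10) or 70% (σ 0.15), and at none of the intakes tried at σ 0.20. With six placebo patients it is a noisy check. All of this stands, and it is why the adjusted ratio should be supportive only.

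Other parts of the plan might seem to cover the gap. Section 9.6.2 says: "Individual values will be listed for each PK parameter by dose level, and the following (non-model-based) descriptive statistics will be provided, if appropriate". Section 9.3 can be read as a between-group comparison. Neither adjusts the ratio. The Day -1 predose and 24 h samples both precede MK-1942, but in the worst case the rise between them is only 4% at 80% intake and 7% at 70%, and they say nothing about change up to Day 21/28.

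The QTcF comparison is only suggestive, since that analysis targets a placebo-adjusted quantity by definition.

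**Conclusion.** The concern holds. The protocol gives placebo a purpose that the donepezil model does not carry out, and the planned GMR cannot separate an MK-1942 effect from a change over time. All of any drift enters the ratio. Pooling the placebo Day 21/28 profiles with Day -1, without a day term, would still leave 92% to 99% of it.

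The likely size is modest and unknown: about 2% from the switch, 1% to 10% with recurring incomplete intake on leave, and 3% to 23% in the worst case. These figures rest on assumed intake and a simple kinetic model, not on trial data. The GMR is secondary, with no margin or test, so the consequence is a possible misattribution and not a wrong decision. The change is worth making because it is cheap and the data are already planned.

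**What to change.** Keep the before/after GMR as the main estimate. Add to Section 9.6.2, and in brief to Section 9.1, one supportive mixed model on log AUC0-24 and log Cmax in both randomised arms at Day -1 and Day 28 (21). It has fixed effects for day and treatment (MK-1942 + donepezil versus donepezil alone, with all Day -1 profiles and the placebo Day 28 (21) profiles as donepezil alone) and a random subject effect. Arm, day and arm-by-day is an alternative with slightly lower precision. Report the Day 28(21)/Day -1 GMR in each arm, and the placebo-adjusted GMR with its 90% CI beside the planned one.

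If only the before/after ratio is wanted, reword Section 4.2.2 so that it no longer assigns placebo this purpose, and describe the GMR as a change from Day -1 not adjusted for time.

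The cost is a few lines of SAP text, with no new samples, visits or patients. The drawback is precision: the adjusted ratio has about 1.7 to 2 times the standard error, so it supports the planned estimate and does not replace it.

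### C_safe in the exploratory concentration-QTc analysis is not limited to observed concentrations, so it can lie above every measured value or have no finite value

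*Combined protocol and SAP*

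**What the plan says.** Section 3 lists the analysis under tertiary/exploratory objectives: "Explore the relationship between plasma concentrations of MK-1942 and corrected QT intervals". The Concentration-QTc text of Section 9.6.2 says "Observed plasma concentrations and observed QTcF change from baseline will be used to investigate the relationship", with placebo concentrations set to zero, and plans scatter plots of QTcF change against time-matched concentration.

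The model is a "linear mixed effects model with fixed effects for treatment (MK-1942, placebo), time point, continuous effects for QTcF baseline, plasma concentration". On the covariance, the text adds: "A double compound symmetry covariance structure will be assumed".

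C_safe is then "defined as the highest drug concentration whose upper limit of the two-sided 90% confidence interval" (described as "equivalent to a one-sided upper 95% confidence limit") of ΔΔQTcF is "less than 10 milliseconds (ms), will be reported". The next sentence adds that the expected mean effect and its 90% CI "will also be computed at the observed geometric mean" Cmax for each dose of interest.

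Section 9.6.3 has a general check of model assumptions, with heteroscedasticity and non-normality as its examples. No section restricts C_safe to the observed range, specifies a check of linearity in concentration, or says what to report if the limit never reaches 10 ms.

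**The concern.** C_safe is found by solving a fitted straight line and its confidence band for a concentration. Such a solution exists whether or not anyone was exposed at that level. If MK-1942 has little effect on QTcF, the band may reach 10 ms only beyond the data. If the estimated slope is clearly negative, it may never do so.

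The flat case is the one the sponsor should expect. Section 4.2.1.1 reports no clinically meaningful ECG changes in studies 001, 002 and 003. The dose is capped at 50 mg BID (Section 1.2, Table 1) and the fourth level is provisional, so the measured range may end lower still.

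What is at stake is a number labelled safe that rests on linearity at exposures no participant had. The data cannot test linearity there, so the general check in Section 9.6.3 does not help. Two analysts following the text could also report different results for the same data, one a large concentration and the other that no value exists.

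**Working it through.** **The one figure in the definition that can be checked.** The normal quantile for the upper end of a two-sided 90% interval is 1.6449, the same as for a one-sided 95% limit. The stated equivalence is correct. The plan gives no C_safe value, QTcF SD or concentration-QTc power.

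**Inputs from the documents.** 18 active and 6 placebo participants; 8, 15, 30 and 50 mg BID for 7 days each (Section 1.2); log-SD of Cmax 0.29 in AD patients (Section 9.9); PK proportional to dose (Section 4.3.2). The footnotes to Section 1.3 give 48 matched ECG and PK times per participant: 7 on each of 5 intense PK days (35), 11 trough days, and 24 and 48 h after the last dose (2).

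**Assumed, because the documents do not state them.** SDs of QTcF change (subject/subject-day/residual) from 4/3/4 to 10/7/8 ms; half-life 6, 8 or 12 h; absorption rate 1.5 per h; baseline QTcF SD 15 ms.

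**Equation.** With treatment intercept a, slope b and generalized least squares variances Va, Vb and covariance Cov, C_safe solves

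a + b·C + 1.6449·√(Va + 2·C·Cov + C²·Vb) = 10.

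**Worked case, estimate exactly flat (a = b = 0).** Take SDs 4/3/4, half-life 6 h, time point as each day-by-hour, and x = C divided by the geometric mean Cmax at the top dose.

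- SE(a) = 2.03, so Va = 4.12. SE(b) on the x scale = 1.33, so Vb = 1.77.
- The upper limit at x = 1 is 3.72, so the variance there is (3.72/1.6449)² = 5.11 and 2·Cov = 5.11 − 4.12 − 1.77 = −0.78.
- The limit reaches 10 ms when the variance is (10/1.6449)² = 36.96. Solving 1.77x² − 0.78x + 4.12 = 36.96 gives x ≈ 4.5 (4.57 when averaged over simulated designs).
- The highest measured concentration averages 4.57/2.54 = 1.80 on this scale, so C_safe is about 2.5 times the maximum.

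With SDs 10/7/8, SE(a) = 5.03, SE(b) = 2.80 and the limit at x = 1 is 8.97. The same steps give x ≈ 1.46, or 0.82 times the maximum. Here the treatment intercept alone takes 1.6449 × 5.03 = 8.27 of the 10 ms, because there are only six placebo participants. At 4/3/4 it takes 1.6449 × 2.03 = 3.34.

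**No true effect, random draws (half-life 8 h).** Ratios are C_safe divided by the highest measured concentration.

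| Time point read as | SDs (ms) | Ratio, flat estimate | Above maximum | Above 3 × maximum | No crossing within 50 × |
|---|---|---|---|---|---|
| day-by-hour | 4/3/4 | 2.5 | 96% | 39% | 5% |
| day-by-hour | 6/4/6 | 1.7 | 75% | 24% | 4% |
| day-by-hour | 8/5/7 | 1.3 | 55% | 16% | 4% |
| day-by-hour | 10/7/8 | 0.8 | 39% | 11% | 3% |
| nominal hour | 4/3/4 | 3.9 | 99% | 66% | 6% |
| nominal hour | 6/4/6 | 2.6 | 86% | 40% | 5% |
| nominal hour | 8/5/7 | 1.9 | 67% | 29% | 4% |
| nominal hour | 10/7/8 | 1.2 | 50% | 19% | 3% |

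A repeat with separate code at the same SDs and half-life gave 52-98% above the maximum, 3-10% with no crossing within 50 times it, and flat-estimate ratios of about 0.8-3.6.

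**Why some trials have no crossing.** At large C the upper limit rises at rate b + 1.6449·SE(b). It never climbs to 10 ms if that rate is zero or negative, that is, if the slope is negative at the one-sided 5% level. With no true effect this happens about 5% of the time by definition, in line with the last column.

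**Sensitivity to the estimated slope (day-by-hour reading).** An estimated effect of −2 ms at the geometric mean Cmax gives ratios from about 1.7 up to no crossing found on the search grid. An estimated +3 ms gives 1.0 or less.

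**The case against.** The analysis is exploratory, with no hypothesis attached. The escalation and stopping rules in Sections 6.6.1 and 6.6.2 do not mention C_safe, and the dose cap is fixed independently of it. The plan also reports the effect and 90% CI at the observed geometric mean Cmax, which lies inside the data. With the scatter plots and the maximum of each PK parameter by dose level, a reader could see whether C_safe lies beyond observed exposure. Section 9.6.2 adds that any broader QTc modelling would have its own Modeling Analysis Plan. All of this stands, and it limits the importance of the point. None of it bounds the number that this study is committed to report.

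A reader might infer that a flat slope necessarily puts C_safe several times above anything measured. That does not follow. The confidence band widens with concentration even at zero slope, and the intercept uses up part of the 10 ms. The flat-estimate ratio runs from below 1 to about 3.9, depending on SDs the documents do not give.

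A reader might also infer that C_safe will set later dose limits. Section 4.3.3 speaks of establishing dosing margins, but no section links C_safe to them or to any dose decision.

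**Conclusion.** The gap is real and minor. As written, the definition can return a concentration above every measured one, or no finite value, when the estimated effect is flat or negative. With no true effect, the first outcome occurs in roughly 40-99% of trials, and roughly 3-10% have no crossing within 50 times the maximum. These ranges rest on assumed QTcF SDs, half-life and absorption rate, on a normal quantile, and on how time point is read; that reading alone moves the flat-estimate ratio about 1.5-fold. That the definition sets no bound can be read from the text and needs none of these assumptions. What the documents support is that C_safe can exceed the observed range, not that it must do so or by several-fold.

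**What to change.** Amend the C_safe sentence in Section 9.6.2. Define C_safe as the highest concentration within the observed range at which the upper limit of the two-sided 90% CI of ΔΔQTcF is below 10 ms. If the limit stays below 10 ms throughout, report that it is below 10 ms up to the highest observed concentration, give that concentration, and report no value beyond it. The ratio to the observed maximum then cannot exceed 1.0, and the no-crossing case has a defined output. It would help to state at the same time whether time point means nominal hour or day-by-hour.

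The change needs one SAP sentence and no extra data. Its price is that the reported C_safe is less favourable and no longer gives a margin beyond observed exposure. Any claim beyond that range would belong in the separate modelling plan that Section 9.6.2 already foresees.
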